7.2.3.3 Protocol-specific Exceptions to Serious Adverse Event Reporting

Efficacy endpoints as outlined in this section will not be reported to the Sponsor as described in Section 7.2.3 - Immediate Reporting of Adverse Events to the Sponsor.

Specifically, the suspected/actual events covered in this exception include any event that is disease progression of the cancer under study.

The eDMC will monitor unblinded aggregated efficacy endpoint events and safety data to ensure the safety of the subjects in the trial. Any suspected endpoint which upon review is not progression of the cancer under study will be forwarded to global safety as a SAE within 24 hours of determination that the event is not progression of the cancer under study.

7.2.4 Evaluating Adverse Events

An investigator who is a qualified physician will evaluate all adverse events according to the NCI Common Terminology for Adverse Events (CTCAE), version 4.0. Any adverse event which changes CTCAE grade over the course of a given episode will have each change of grade recorded on the adverse event case report forms/worksheets.

All adverse events regardless of CTCAE grade must also be evaluated for seriousness.

For studies in which multiple agents are administered as part of a combination regimen, the investigator may attribute each adverse event causality to the combination regimen or to a single agent of the combination. In general, causality attribution should be assigned to the combination regimen (i.e., to all agents in the regimen). However, causality attribution may be assigned to a single agent if in the investigator's opinion, there is sufficient data to support full attribution of the adverse experience to the single agent.

Table 15 Evaluating Adverse Events

An investigator who is a qualified physician, will evaluate all adverse events as to:

V4.0 CTCAE Grading	Grade 1	Mild; asymptomatic or mild symptoms; clinical or diagnostic observations only; intervention not indicated.
	Grade 2	Moderate; minimal, local or noninvasive intervention indicated; limiting age-appropriate instrumental ADL.
	Grade 3	Severe or medically significant but not immediately life-threatening; hospitalization or prolongation of hospitalization indicated; disabling; limiting self-care ADL.
	Grade 4	Life threatening consequences; urgent intervention indicated.
	Grade 5	Death related to AE
Seriousness	A serious adverse event is any adverse event occurring at any dose or during any use of Sponsor's product that:	
	† Results in death ; or	
	† Is life threatening ; or places the subject, in the view of the investigator, at immediate risk of death from the event as it occurred (Note: This does not include an adverse event that, had it occurred in a more severe form, might have caused death.); or	
	† Results in a persistent or significant disability/incapacity (substantial disruption of one's ability to conduct normal life functions); or	
	† Results in or prolongs an existing inpatient hospitalization (hospitalization is defined as an inpatient admission, regardless of length of stay, even if the hospitalization is a precautionary measure for continued observation. (Note: Hospitalization for an elective procedure to treat a pre-existing condition that has not worsened is not a serious adverse event. A pre-existing condition is a clinical condition that is diagnosed prior to the use of a Merck product and is documented in the patient's medical history.); or	
	† Is a congenital anomaly/birth defect (in offspring of subject taking the product regardless of time to diagnosis); or	
	Is a new cancer (that is not a condition of the study) (although not serious per ICH definition, is reportable to the Sponsor within 24 hours to meet certain local requirements); or	
	Is an overdose (whether accidental or intentional). Any adverse event associated with an overdose is considered a serious adverse event for collection purposes. An overdose that is not associated with an adverse event is considered a non-serious event of clinical interest and must be reported within 24 hours.	
	Other important medical events that may not result in death, not be life threatening, or not require hospitalization may be considered a serious adverse event when, based upon appropriate medical judgment, the event may jeopardize the subject and may require medical or surgical intervention to prevent one of the outcomes listed previously (designated above by a †).	
Duration	Record the start and stop dates of the adverse event. If less than 1 day, indicate the appropriate length of time and units	
Action taken	Did the adverse event cause the Sponsor's product to be discontinued?	
Relationship to Sponsor's Product	Did the Sponsor's product cause the adverse event? The determination of the likelihood that the Sponsor's product caused the adverse event will be provided by an investigator who is a qualified physician. The investigator's signed/dated initials on the source document or worksheet that supports the causality noted on the AE form, ensures that a medically qualified assessment of causality was done. This initialed document must be retained for the required regulatory time frame. The criteria below are intended as reference guidelines to assist the investigator in assessing the likelihood of a relationship between the test drug and the adverse event based upon the available information. The following components are to be used to assess the relationship between the Sponsor's product and the AE; the greater the correlation with the components and their respective elements (in number and/or intensity), the more likely the Sponsor's product caused the adverse event (AE):	
	Exposure	Is there evidence that the subject was actually exposed to the Sponsor's product such as: reliable history, acceptable compliance assessment (pill count, diary, etc.), expected pharmacologic effect, or measurement of drug/metabolite in bodily specimen?
	Time Course	Did the AE follow in a reasonable temporal sequence from administration of the Sponsor's product? Is the time of onset of the AE compatible with a drug-induced effect (applies to trials with investigational medicinal product)?
	Likely Cause	Is the AE not reasonably explained by another etiology such as underlying disease, other drug(s)/vaccine(s), or other host or environmental factors

Relationship to Sponsor's Product (continued)	The following components are to be used to assess the relationship between the test drug and the AE: (continued)	
	Dechallenge	Was the Sponsor's product discontinued or dose/exposure/frequency reduced? If yes, did the AE resolve or improve? If yes, this is a positive dechallenge. If no, this is a negative dechallenge. (Note: This criterion is not applicable if: (1) the AE resulted in death or permanent disability; (2) the AE resolved/improved despite continuation of the Sponsor's product; or (3) the trial is a single-dose drug trial; or (4) Sponsor's product(s) is/are only used one time.)
	Rechallenge	Was the subject re-exposed to the Sponsor's product in this study? If yes, did the AE recur or worsen? If yes, this is a positive rechallenge. If no, this is a negative rechallenge. (Note: This criterion is not applicable if: (1) the initial AE resulted in death or permanent disability, or (2) the trial is a single-dose drug trial); or (3) Sponsor's product(s) is/are used only one time). NOTE: IF A RECHALLENGE IS PLANNED FOR AN ADVERSE EVENT WHICH WAS SERIOUS AND WHICH MAY HAVE BEEN CAUSED BY THE SPONSOR'S PRODUCT, OR IF REEXPOSURE TO THE SPONSOR'S PRODUCT POSES ADDITIONAL POTENTIAL SIGNIFICANT RISK TO THE SUBJECT, THEN THE RECHALLENGE MUST BE APPROVED IN ADVANCE BY THE SPONSOR CLINICAL DIRECTOR AS PER DOSE MODIFICATION GUIDELINES IN THE PROTOCOL.
	Consistency with Trial Treatment Profile	Is the clinical/pathological presentation of the AE consistent with previous knowledge regarding the Sponsor's product or drug class pharmacology or toxicology?
The assessment of relationship will be reported on the case report forms /worksheets by an investigator who is a qualified physician according to his/her best clinical judgment, including consideration of the above elements.		
Record one of the following	Use the following scale of criteria as guidance (not all criteria must be present to be indicative of a Sponsor's product relationship).	
Yes, there is a reasonable possibility of Sponsor's product relationship.	There is evidence of exposure to the Sponsor's product. The temporal sequence of the AE onset relative to the administration of the Sponsor's product is reasonable. The AE is more likely explained by the Sponsor's product than by another cause.	
No, there is not a reasonable possibility of Sponsor's product relationship	Subject did not receive the Sponsor's product OR temporal sequence of the AE onset relative to administration of the Sponsor's product is not reasonable OR the AE is more likely explained by another cause than the Sponsor's product. (Also entered for a subject with overdose without an associated AE.)	

7.2.5 Sponsor Responsibility for Reporting Adverse Events

All Adverse Events will be reported to regulatory authorities, IRB/IECs and investigators in accordance with all applicable global laws and regulations, i.e., per ICH Topic E6 (R1) Guidelines for Good Clinical Practice.

7.3 TRIAL GOVERNANCE AND OVERSIGHT

7.3.1 Scientific Advisory Committee

This trial was developed in collaboration with a Scientific Advisory Committee (SAC). The SAC comprises both Sponsor and non-Sponsor scientific experts who provide input with respect to trial design, interpretation of trial results and subsequent peer-reviewed scientific publications.

7.3.2 Executive Oversight Committee

The Executive Oversight Committee (EOC) comprises members of Sponsor Senior Management. The EOC will receive and decide upon any recommendations made by the Data Monitoring Committee (DMC) regarding the trial.

7.3.3 Data Monitoring Committee

An external Data Monitoring Committee (eDMC) will be formed prior to study start to periodically monitor safety and evaluate the interim data from this trial. The members of the committee are external to the Sponsor, are not involved with the trial in any other way (e.g., they cannot be trial investigators) and have no competing interests that could affect their roles with respect to the trial.

The eDMC will make recommendations to the EOC regarding steps to ensure both subject safety and the continued ethical integrity of the trial. Also, the eDMC will review interim trial results, consider the overall risk and benefit to trial participants (see Section 8.7 - Interim Analyses) and recommend to the EOC if the trial should continue in accordance with the protocol.

Specific details regarding composition, responsibilities, and governance, including the roles and responsibilities of the various members and the Sponsor protocol team; meeting facilitation; the trial governance structure; and requirements for and proper documentation of DMC reports, minutes, and recommendations will be described in the eDMC charter that is reviewed and approved by all the eDMC members.

8.0 STATISTICAL ANALYSIS PLAN

This section outlines the statistical analysis strategy and procedures for the study. If, after the study has begun, changes are made to primary and/or key secondary hypotheses, or the statistical methods related to those hypotheses, then the protocol will be amended (consistent with ICH Guideline E-9). Changes to exploratory or other non-confirmatory analyses made after the protocol has been finalized, but prior to the conduct of any analysis, will be documented in a supplemental (sSAP) and referenced in the Clinical Study Report (CSR) for the study. Separate analysis plans may be developed for PK/modeling analysis,

biomarker analysis, and genetic data analysis. Post hoc exploratory analyses will be clearly identified in the CSR. The PRO analysis plan will be included in the sSAP.

8.1 Statistical Analysis Plan Summary

Key elements of the statistical analysis plan are summarized below; the comprehensive plan is provided in Sections 8.2 through 8.12.

Study Design Overview	This is a randomized, open-label, multicenter Phase III trial to evaluate efficacy and safety of pembrolizumab in combination with axitinib versus sunitinib monotherapy as a first-line treatment for locally advanced or mRCC.
Treatment Assignment	Approximately 840 subjects will be randomized 1:1 into the following two treatment arms: Arm 1 will receive the combination therapy of pembrolizumab 200 mg administered intravenously (IV) every 3 weeks (Q3W) and axitinib 5 mg twice daily (BID) taken orally; Arm 2 will receive sunitinib monotherapy 50 mg daily (QD) taken orally for 4 weeks then off treatment for 2 weeks. Stratification factors are provided in Section 5.4. This is an open-label study.
Analysis Populations	Efficacy: Intention to Treat (ITT) Safety: All Subjects as Treated (ASaT)
Primary Endpoints	1. Progression-free survival (PFS), per RECIST 1.1 by BICR review 2. Overall survival (OS)
Statistical Methods for Key Efficacy Analyses	The primary hypotheses for PFS and OS will be evaluated by comparing pembrolizumab in combination with axitinib to sunitinib using a stratified log-rank test. Estimation of the hazard ratio will be done using a stratified Cox regression model. Event rates over time will be estimated within each treatment group using the Kaplan-Meier method. Stratified Miettinen and Nurminen's method with weights proportional to the stratum size will be used for comparison of the objective response rates (ORR) between the treatment arms.
Statistical Methods for Key Safety Analyses	The analysis of safety results will follow a tiered approach. The tiers differ with respect to the analyses that will be performed. There are no Tier 1 events in this trial. Tier 2 parameters will be assessed via point estimates with 95% confidence intervals provided for between-group comparisons; only point estimates by treatment group are provided for Tier 3 safety parameters. The 95% confidence intervals for the between-treatment differences in percentages will be provided using the Miettinen and Nurminen method.


Interim and Final Analyses
	
Two interim analyses are planned for the study. Results will be reviewed by an external data monitoring committee (eDMC). Details are provided in Section 8.7.
 
 • First Interim Analysis (IA1) 
 ○ Timing: To be performed after enrollment completion, once a 7-month minimum follow up (ie, 7 months since last subject is randomized) has been achieved and a minimum of 305 PFS events have accrued. It is expected to be 22 months after the first subject randomized (study start). Approximately 48% of the final required OS events (or 195 deaths) are expected at that time. ○ Purpose: First interim analysis for PFS and OS. • Second Interim Analysis (IA2) 
 ○ Timing: To be performed when approximately 74% of the final required OS events (or 299 deaths) have accrued, expected to be 31 months after study start. At IA2, approximately 487 PFS events are expected. ○ Purpose: Final analysis for PFS and IA2 for OS. • Final analysis (event-driven trial) 
 ○ Timing: When approximately 404 deaths have accrued, expected to be 43 months after study start. ○ Purpose: Final analysis for OS (assuming not declared successful at the interim analysis)

Multiplicity
	
The overall Type I error rate is strongly controlled at 2.5% (1-sided) with 0.2% initially allocated to PFS and 2.3% initially allocated to OS. A group sequential approach will be used to allocate alpha between the interim and final analyses. The study will be considered a success if either PFS or OS is demonstrated to be statistically significant under multiplicity control. Note that the study would continue for OS even if PFS is shown to be statistically significant at IA1 or IA2.

Sample Size and Power
	
The sample size was planned for 840 but the following power calculations are based on the actual final number of randomized subjects (N = 861). There are 2 primary endpoints for this study, PFS, and OS. The expected median PFS time in the control group is 13 months. Based on 487 PFS events, the study has ~99% power to detect a hazard ratio of 0.60 for PFS (pembrolizumab+axitinib combination vs. sunitinib) at alpha=0.2% (1-sided). The expected median OS time in the control group is 33 months. Based on 404 death events, the study has 80% power to detect a hazard ratio of 0.75 for OS at alpha=2.3% (1-sided).

8.2 Responsibility for Analyses/In-house Blinding

The statistical analysis of the data obtained from this study will be the responsibility of the Clinical Biostatistics department of the Sponsor.

The Sponsor will generate the randomized allocation schedule(s) for study treatment assignment for this protocol, and the randomization will be implemented in IVRS.

Although the trial is open label, analyses or summaries generated by randomized treatment assignment and/or actual treatment received will be limited and documented. Further documentation will be provided in the sSAP. In addition, independent central imaging review will be performed without knowledge of the treatment group assignments of the subjects.

The eDMC will serve as the primary reviewer of the unblinded results of the PFS and OS at interim analyses and may make recommendations for discontinuation of the study or modification to an EOC of the Sponsor. Depending on the recommendations of the eDMC, the Sponsor may prepare a regulatory submission. If the eDMC recommends modifications to the design of the protocol or discontinuation of the study, the EOC may be unblinded to results at the treatment level in order to evaluate and direct the Sponsor protocol team as to the appropriate actions to be taken on these recommendations. Additional logistical details, revisions to the above plan, and data monitoring guidance will be provided in the DMC Charter.

8.3 Hypotheses/Estimation

Objectives and hypotheses of the study are stated in Section 3.0.

8.4 Analysis Endpoints

8.4.1 Efficacy Endpoints

8.4.1.1 Primary

Progression-free Survival (PFS) – RECIST 1.1 by Blinded Central Imaging Vendor Review

Progression-free survival is defined as the time from randomization to the first documented disease progression per RECIST 1.1 based on BICR or death due to any cause, whichever occurs first. See Section 8.6.1 for the censoring rules.

Overall Survival (OS)

Overall survival is defined as the time from randomization to death due to any cause. Subjects without documented death at the time of the final analysis will be censored at the date of the last follow up.

8.4.1.2 Secondary

Objective Response Rate (ORR) – RECIST 1.1 by BICR

Objective response rate is defined as the proportion of the subjects in the analysis population who have a CR or PR per RECIST 1.1.

Duration of Response (DOR) - RECIST 1.1 by BICR

For subjects who demonstrate CR or PR, DOR is defined as the time from first documented evidence of CR or PR per RECIST 1.1 until disease progression per RECIST 1.1 or death due to any cause, whichever occurs first. See Section 8.6.1 for the censoring rules.

Disease Control Rate (DCR) - RECIST 1.1 by BICR

Disease control rate is defined as the percentage of subjects who have achieved CR, PR, or SD of ≥ 6 months based on assessments by BICR per RECIST 1.1.

8.4.2 Safety Endpoints

Safety endpoints are described in Sections 4.2.3.2.

8.5 Analysis Population

8.5.1 Efficacy Analysis Population

The Intention-to-Treat (ITT) population will serve as the population for the primary efficacy analyses. All randomized subjects will be included in this population. Subjects will be analyzed in the treatment group to which they are randomized. Details on the approach to handling missing data are provided in Section 8.6.1 – Statistical Methods for Efficacy Analyses.

The analysis population of DOR consists of responders.

8.5.2 Safety Analysis Population

The All Subjects as Treated (ASaT) population will be used for the analysis of safety data in this study. The ASaT population consists of all randomized subjects who received at least 1 dose of study treatment. Subjects will be analyzed in the treatment group corresponding to the study treatment they actually received for the analysis of safety data using the ASaT population. For most subjects this will be the treatment group to which they are randomized. Subjects who take incorrect study treatment for the entire treatment period will be included in the treatment group corresponding to the study treatment actually received. Any subject who receives the incorrect study medication for one cycle but receives the correct treatment for all other cycles will be analyzed according to the correct treatment group and a narrative will be provided for any events that occur during the cycle for which the subject is incorrectly dosed.

At least 1 laboratory or vital sign measurement obtained subsequent to at least 1 dose of study treatment is required for inclusion in the analysis of each specific parameter. To assess change from baseline, a baseline measurement is also required.

8.6 Statistical Methods

8.6.1 Statistical Methods for Efficacy Analyses

This section describes the statistical methods that address the primary and secondary objectives. Methods related to exploratory objectives will be described in the sSAP.

Efficacy results that will be deemed to be statistically significant after consideration of the Type I error control strategy are described in Section 8.8, Multiplicity. Nominal p-values may be computed for other efficacy analyses, but should be interpreted with caution due to potential issues of multiplicity.

8.6.1.1 Progression-free Survival

The non-parametric Kaplan-Meier method will be used to estimate the PFS curve in each treatment group including the PFS rates at 12, 18, and 24 months (based on data adequacy). The treatment difference in PFS will be assessed by the stratified log-rank test. A stratified Cox proportional hazard model with Efron's method of tie handling will be used to estimate the magnitude of the treatment difference (i.e., hazard ratio) between the treatment arms. The hazard ratio and its 95% confidence interval from the stratified Cox model with Efron's method of tie handling and with a single treatment covariate will be reported. The stratification factors used for randomization (see Section 5.4) will be applied to both the stratified log-rank test and the stratified Cox model.

Since disease progression is assessed periodically, progressive disease (PD) can occur any time in the time interval between the last assessment where PD was not documented and the assessment when PD is documented. The true date of disease progression will be approximated by the date of the first assessment at which PD is objectively documented per RECIST 1.1 by BICR. Death is always considered as a confirmed PD event. Subjects who do not experience a PFS event will be censored at the last disease assessment. Sensitivity analyses will be performed for comparison of PFS based on investigator's assessment and PFS with PD determined per irRECIST by BICR, as indicated in the exploratory objectives.

In order to evaluate the robustness of the PFS endpoint per RECIST 1.1 by BICR, one primary and two sensitivity analyses with a different set of censoring rules will be performed. For the primary analysis, if PD or death events occur immediately after more than one missing disease assessment, the PFS data are censored at the last disease assessment prior to the missing visits. Also, data after new anti-cancer therapy are censored at the last disease assessment prior to the initiation of new anti-cancer therapy.

The first sensitivity analysis follows the intention-to-treat principle. That is, PDs/deaths are counted as events regardless of missed study visits or initiation of new anti-cancer therapy. The second sensitivity analysis considers discontinuation of treatment due to reasons other than complete response or initiation of new anti-cancer treatment (whichever occurs later) to be a PD event for subjects without documented PD or death. If a subject meets multiple criteria for censoring, the censoring criterion that occurs earliest will be applied. The censoring rules for primary and sensitivity analyses are summarized in [Table 16](#).

Table 16 Censoring Rules for Primary and Sensitivity Analyses of PFS

Situation	Primary Analysis	Sensitivity Analysis 1	Sensitivity Analysis 2
PD or death documented after ≤ 1 missed disease assessment, and before new anti-cancer therapy, if any	Progressed at date of documented PD or death	Progressed at date of documented PD or death	Progressed at date of documented PD or death
PD or death documented immediately after ≥ 2 consecutive missed disease assessments or after new anti-cancer therapy, if any	Censored at last disease assessment prior to the earlier date of ≥ 2 consecutive missed disease assessment and new anti-cancer therapy, if any	Progressed at date of documented PD or death	Progressed at date of documented PD or death
No PD and no death; and new anticancer treatment is not initiated	Censored at last disease assessment	Censored at last disease assessment	Progressed at treatment discontinuation due to reasons other than complete response; otherwise censored at last disease assessment if still on study treatment or completed study treatment.
No PD and no death; new anticancer treatment is initiated	Censored at last disease assessment before new anticancer treatment	Censored at last disease assessment	Progressed at date of new anticancer treatment

PD = progressive disease; PFS = progression-free survival.

The proportional hazards assumption on PFS will be examined using both graphical and analytical methods if warranted. The log [-log] of the survival function vs. time for PFS will be plotted for the comparison between pembrolizumab+axitinib combination and the control arm. If the curves are not parallel, indicating that hazards are not proportional, supportive analyses may be conducted to account for the possible non-proportional hazards effect associated with immunotherapies. Further details of sensitivity analyses will be described in the SAP.

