8.5.2	Safety Analysis Population	Deleted the last sentence: “Details on the approach to handling missing data for safety analyses are provided in Section 8.6.2 Statistical Methods for Safety Analysis.	The sentence is no longer needed.
8.6.1.1	Progression-free Survival	Added the estimation for landmark PFS rates. Updated the censoring rules for primary and sensitivity analyses of PFS.	To provide the statistical method for the added secondary objective on landmark PFS rates. To be aligned with the recent changes in the therapeutic standard PFS censoring rules; the primary analysis closely follows FDA guidance; and the first sensitivity analysis closely follows the “intent-to-treat (ITT) complete follow-up principle”.
8.6.1.2	Overall Survival	Added the estimation for landmark OS rates.	To provide the statistical method for the added secondary objective on landmark OS rates.

Section Number (s)	Section Title (s)	Description of Change (s)	Rationale
8.6.1.4	Duration of Response	Updated the censoring rules for primary and sensitivity analyses of DOR.	To be aligned with the updated censoring rule for PFS.
8.6.1.6	Summary of Statistical Methods for efficacy	This is a new section header added after the first paragraph of previous section 8.6.1.5. In Table 18, header of the last column is changed from “missing data approach” to “missing data / censoring approach	The header was inserted to clarify the purpose for the table.
8.6.2	Statistical Methods for Safety Analyses	Updated the criterion for Tier 2 safety events and updated the list of additional events to be considered as Tier 2 or Tier 3 safety events.	Subjects enrolled in this study usually experience various adverse events of similar types, adverse events reported less frequent than in 10% or SAE, Grade 3-5 events reported in less than 5% of subjects would obscure the assessment of overall safety profile and add little to meaningful interpretation.
8.7	Interim Analyses	Editorial changes in Table 20.	To be more aligned with text in Section 8.7 and 8.8.
8.9	Sample Size and Power Calculations	Power statement is updated for PFS and OS endpoints.	Power statement has been changed using actual number of randomized subjects with updated median assumptions in the control arm based on emerging data.
8.10	Subgroup Analyses and Effect of Baseline Factors	Pre-specified each subgroup category and provided source where PD-L1 cutpoint has been selected.	To be more specific and clear.

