7.1.2.7.3 End of Treatment and Follow-up Tumor Imaging

Subjects who discontinue treatment for reasons other than BICR verified PD should continue with imaging assessments per the protocol-defined schedule until PD is BICR verified or further confirmed by investigator (i.e., following PD verification by BICR), initiation of a new anti-cancer treatment, death, withdrawal of consent or study conclusion/early termination, whichever occurs first. See Section 7.1.5.3.3 for more details.

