7.1.5.3.4 Survival Follow-up Visits

Subjects who experience PD that is verified by BICR or further confirmed by the investigator or start a new anticancer therapy, will move into the Survival Follow-up Phase and should be contacted by telephone approximately every 12 weeks to assess for survival status until death, withdrawal of consent, or the end of the trial, whichever occurs first.

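### Does PFS Sensitivity Analysis 2 go wrong by dating an event at treatment stop or new therapy only when no progression or death has been documented?

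*Combined protocol and SAP*

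**What the plan says.** Section 8.6.1.1 announces that "one primary and two sensitivity analyses with a different set of censoring rules will be performed", to examine how robust BICR-assessed PFS is. Table 16 gives the rules as four situations.

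- **Progression or death documented (rows 1 and 2).** Sensitivity Analysis 2 is identical to Sensitivity Analysis 1. The event is at the documented date, even after missed assessments or new therapy.
- **Neither documented, no new therapy (row 3).** The event part reads "Progressed at treatment discontinuation due to reasons other than complete response". For the remaining patients in this row the entry is "otherwise censored at last disease assessment if still on study treatment or completed study treatment".
- **Neither documented, new therapy started (row 4).** "Progressed at date of new anticancer treatment".

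The text agrees with the table: a stop or new therapy is "initiation of new anti-cancer treatment (whichever occurs later) to be a PD event for subjects without documented PD or death". The sentence in the same section that applies the earliest criterion concerns censoring criteria only, so it does not reorder these events.

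Follow-up goes on after a stop. Section 7.1.2.7.3 states: "Subjects who discontinue treatment for reasons other than BICR verified PD should continue with imaging assessments per the protocol-defined schedule". Under Section 7.1.5.3.4, patients who "start a new anticancer therapy, will move into the Survival Follow-up Phase and should be contacted by telephone approximately every 12 weeks", so a death can still be recorded.

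**The concern.** Take two patients who both stop for an adverse event at month 6. Patient A progresses at month 20, so the event is at month 20. Patient B has clean scans to month 30, so the event is at month 6. The patient who did better gets the earlier failure, and that failure precedes scans showing no progression. The rule uses information from after month 6 to decide what happened at month 6, which one normally avoids in time-to-event work.

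The date is also not stable. A patient who stops at month 4 and progresses at month 10 is dated at month 4 if the cutoff falls at that patient's month 8, and at month 10 if it falls at month 14.

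The Summary of Changes adds to the unease. It explains the revised rules with "To be aligned with the recent changes in the therapeutic standard PFS censoring rules; the primary analysis closely follows FDA guidance" and gives a principle for Sensitivity Analysis 1, but none for Sensitivity Analysis 2. If the rule were incoherent, one of the two planned checks on the BICR PFS result would be hard to interpret.

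**Working it through.** **1. What the rule changes.** Section 8.4.1.1 defines PFS as time to BICR-documented progression or death. Set side by side, the two sensitivity columns of Table 16 differ only in rows 3 and 4. Sensitivity Analysis 1 censors there; Sensitivity Analysis 2 imputes a failure, except for row 3 patients who are still on treatment, have completed it, or stopped for complete response. Every observed endpoint stays where it was observed. The rule therefore asks how the result would look if patients who left treatment without a documented endpoint had in fact failed when they left. That is a stress test of informative censoring. Patient A needs no imputation because the progression date is known. Patient B has no endpoint on record and gets the pessimistic value.

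**2. What the alternative would do.** The alternative dates everyone at the earliest of progression, death, non-CR stop or new therapy. The documents give no stop rate for the whole regimen, so the rates here are assumptions. Simulation inputs:

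- From Section 8.9: 861 patients, 15 months of accrual, exponential PFS, control median 13 months, hazard ratio 0.60, 10% yearly dropout.
- Assumed: stops independent of progression, imaging continuing after a stop, no new therapy; unstratified Cox model.

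The simulation gives about 358 PFS events at month 22 (plan: 365) and about 484 at month 31 (plan: 487), so it matches the design.

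At yearly stop rates of 20% (combination) and 12% (sunitinib), month 31:

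| | Rule as written | Earliest-event rule |
|---|---|---|
| Patients stopping before progression or death | 151 | 151 |
| Dated at the stop | 93 | 151 |
| Dated at documented progression or death | 58 | 0 |

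The 58 stopped at a mean of 6.8 months and had their event at a mean of 14.1. The alternative would date them 14.1 − 6.8 = 7.3 months before the observed endpoint. If the complaint is that failures are placed ahead of progression-free follow-up, the alternative does this to 58 more patients.

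**3. Size of the difference.** Hazard ratio under the earliest-event rule minus hazard ratio as written, month 31, dropout censored:

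| Yearly stop rate, combination / sunitinib | Difference |
|---|---|
| 25% / 12% | +0.026 |
| 20% / 12% | +0.015 |
| 15% / 12% | +0.006 |
| 10% / 10% | 0.000 |
| 20% / 20% | −0.002 |
| 12% / 20% | −0.012 |
| 12% / 25% | −0.018 |

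Coding dropout on treatment as a row 3 event changes these by at most about 0.003. At 20%/12% the gap is about 0.02 on the log scale, against a standard deviation of 0.08 to 0.09 for the estimate itself. In the same scenario the rule as written already moves the hazard ratio from the assumed 0.60 to 0.781, a shift of 0.181, against 0.015 between the two versions.

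**4. Re-dating between cutoffs.** Under Sections 2.1 and 8.7, PFS is formally tested at month 31 only if it was not significant at the first interim analysis. Power is Φ(½√d·|ln HR| − z), with |ln 0.60| = 0.5108.

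- Final analysis, 487 events, one-sided alpha 0.2%: ½√487 × 0.5108 = 5.636; 5.636 − 2.878 = 2.758; power 0.997. The plan says about 99%.
- First interim, 365 events, Table 20 boundary Z = 3.06: ½√365 × 0.5108 = 4.880; 4.880 − 3.06 = 1.820; power 0.966. Table 20 says about 96.5%.

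Under the design hazard ratio, a second formal PFS test follows with probability about 100% − 96.5% = 3.5%. At the 305-event minimum, Section 8.7 promises at least 90% power, so the figure is then at most 10%. If Sensitivity Analysis 2 is nevertheless run at both cutoffs, about a quarter of the stop-dated patients move (22 of 85 at 20%/12%), by a mean of 11.8 months. In each case an imputed date gives way to an observed one.

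**The case for a change.** The strongest opposing point is that Patient B's outcome is not wholly unknown. The scans to month 30 were read and show no progression, yet row 3 places the failure at month 6 rather than after the last clean scan. Dates that depend on later data also mean that the resulting hazard ratio does not describe any single well-defined event process. An earliest-event rule is free of that dependence and stable across cutoffs, and the change could be recorded in the supplemental SAP at little cost.

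The description is accurate, and the hazard ratio from this analysis should not be reported as an effect estimate in its own right. But the harshness of row 3 is what makes it a stress test, and Sensitivity Analysis 1, reported beside it, already treats Patient B as progression-free to the last scan. The earliest-event rule gains its stability by replacing observed BICR progressions with treatment stops. That makes it a treatment-failure composite and no longer a check on BICR PFS. A sponsor might reasonably want that analysis as well; its absence is not an error.

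The missing rationale is a fair remark but a small one. Section 8.6.1.1 states the purpose of both sensitivity analyses, and the Summary of Changes attributes the revised PFS censoring rules to a therapeutic-area standard. A change log that does not explain every column is weak evidence of a defect.

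**Conclusion.** The concern does not hold. Text and table agree, and the rule is coherent for its purpose: observed progressions and deaths stand, and failure is imputed only where the first sensitivity analysis censors. Preferring an earliest-event composite is a choice of a different target, on which reasonable statisticians will differ.

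The difference between the two versions is about 0.03 or less in hazard ratio in every scenario examined, with a sign that depends on which arm stops more. This size rests on assumed stop rates, on stops independent of progression and on leaving new therapy out, so row 4 was not quantified. The argument from the structure of Table 16 needs none of these assumptions. Whatever the true rates, no decision uses Sensitivity Analysis 2, and the primary PFS test, alpha split, boundaries, power and Sensitivity Analysis 1 are unaffected.
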